### **Special Consideration**

#### *Lesions by clinical examination*

Lesions by clinical examination will not be used for response in this study.

#### *Cystic lesions*

- Cystic lesions that meet the criteria for radiographically defined simple cysts should not be considered as malignant lesions (neither measurable nor nonmeasurable) since they are, by definition, simple cysts.
- Cystic lesions thought to represent cystic metastases can be considered as measurable lesions, if they meet the definition of measurability described above. However, if noncystic lesions are present in the same patient, these are preferred for selection as target lesions.

#### *Bone lesions*

- Bone scan, PET scan or plain films are not considered adequate imaging techniques to measure bone lesions. However, these techniques can be used to confirm the presence or disappearance of bone lesions.
- Lytic bone lesions or mixed lytic-blastic lesions, with identifiable soft tissue components, that can be evaluated by cross-sectional imaging techniques such as CT or MRI can be considered as measurable lesions if the *soft tissue component* meets the definition of measurability described above.
- Blastic bone lesions are non-measurable.

### *Lesions with prior local treatment*

- Lesions situated in a previously irradiated area, or in an area subjected to other loco-regional therapy, are not considered measurable.

### **Imaging Methods**

The same method of assessment and the same technique used to characterize each identified and reported lesions at baseline should be used during each follow-up assessment. All measurements should be taken and recorded in metric notation using a ruler or calipers. Imaging based evaluation is preferred to evaluation by clinical examination unless the lesion(s) being followed cannot be imaged but assessed by clinical examination (referring to biopsy-proven visible lesion(s) on the chest).

Chest x-ray: Chest x-ray will not be used for response assessment in this study.

Conventional CT and MRI: This guideline has defined measurability of lesions on CT scan based on the assumption that CT slice thickness is 5 mm or less. If CT scans have slice thickness greater than 5 mm, the minimum size for a measurable lesion is twice the slice thickness. MRI is also acceptable in certain situations (eg, for body scan) except for lung.

Use of MRI remains a complex issue. MRI has excellent contrast, spatial, and temporal resolution; however, there are many image acquisition variables involved in MRI, which greatly impact image quality, lesion conspicuity, and measurement. Furthermore, the availability of MRI is variable globally. As with CT, if an MRI is performed, the technical specifications of the scanning sequences used should be optimized for the evaluation of the type and site of disease. Furthermore, as with CT, the modality used at follow-up should be the same as was used at baseline and the lesions should be measured/assessed on the same pulse sequence. It is beyond the scope of the RECIST guidelines to prescribe specific MRI pulse sequence parameters for all scanners, body parts, and diseases. Ideally, the same type of scanner should be used and the image acquisition protocol should be followed as closely as possible to prior scans. Body scans should be performed with breath-hold scanning techniques, if possible.

Positron emission tomography will not be used for response assessment in this study.

Ultrasound: Ultrasound will not be used for response assessment in this study

Bone scans will be used to assess the presence or disappearance of the bone component of bone lesions. CT or MRI scan will be used to confirm ambiguous results of bone scans. Preferred method for confirmation is MRI.

Tumor Markers: Tumor markers may be evaluated for changes but will not be used to determine progressive disease in this study.

Cytology, Histology: The cytological confirmation of the neoplastic origin of any effusion that appears or worsens during treatment when the measurable tumor has met criteria for response or stable disease will be considered malignant unless cytologically confirmed.

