### ***Liver decompensation***

- GI bleeding, hepatic encephalopathy, ascites, and bacterial infections should be treated as in patients with nonneoplastic liver disease

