### Definitions

Baseline: Baseline is defined as the most recent assessment performed prior to randomization. Baseline assessments must be performed within the period defined in the protocol eligibility criteria.

Measurable lesions: Except for lymph nodes as described below, measurable lesions are defined as those that can be accurately measured in at least 1 dimension (longest diameter to be recorded) as  $\geq 10$  mm with CT scan (if CT scans have slice thickness greater than 5 mm the minimum size for a measurable lesion is twice the slice thickness).

- To be considered pathologically enlarged and measurable, a lymph node must be  $\geq 15$  mm in short axis when assessed by CT scan (CT scan slice thickness recommended to be no greater than 5 mm). At baseline and in follow-up, only the short axis will be measured and recorded.
- MRI may be substituted for contrast-enhanced CT for lesions at some anatomical sites, but not for lesions in the lungs. The minimum size for measurability is the same as for CT (10 mm) as long as the scans are performed with slice thickness of 5 mm and no gap. If MRI is performed with thicker slices, the size of a measurable lesion at baseline should be twice the slice thickness. In the event there are interslice gaps, this also needs to be considered in determining the size of measurable lesions at baseline.

Nonmeasurable lesions: All other lesions (or sites of disease), including small lesions (longest diameter  $< 10$  mm or pathological lymph nodes with  $\geq 10$  to  $< 15$  mm short axis), are considered nonmeasurable. Lymph nodes that have a short axis  $< 10$  mm are considered nonpathological and are not be recorded or followed. Bone lesions, leptomeningeal disease, ascites, pleural/pericardial effusions, lymphangitis cutis/ pulmonitis, inflammatory breast disease, and abdominal masses (not followed by CT or MRI), are considered as nonmeasurable.

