### **Time Point Assessments**

The frequency and schedule of tumor assessments is defined in the protocol. The schedule is to be maintained regardless of whether study treatment is held or discontinued.

At baseline, tumors and lymph nodes are classified and documented as target or nontarget per the definitions provided above. It is possible to record multiple nontarget lesions involving the same organ as a single item (eg, ‘multiple liver metastases’).

At all postbaseline (follow-up) evaluations the baseline classification (target, nontarget) is to be maintained and lesions are to be documented and described in a consistent fashion over time (eg, recorded in the same order on source documents).

At each assessment, a sum of the diameters (longest for nonnodal lesions, short axis for nodal lesions) for all target lesions will be calculated and included in source documents. The *baseline sum of the diameters* (SoD) will be used as reference to further characterize any objective tumor regression in the measurable dimension of the disease. The lowest SoD (nadir) since (and including) the baseline value will be used as reference for evaluating progression.

After baseline, target lesions should have the actual size documented, if possible, even if the lesions become very small. If in the opinion of the radiologist the lesion has likely disappeared, 0 mm should be recorded. If the lesion is present but too small to measure, an indicator for ‘too small to measure’ should be included in source documents.

Nontarget lesions are to be assessed qualitatively (present, resolved, or unequivocal progression) and new lesions, if any, are to be documented separately.

At each evaluation, progression status is to be determined based upon the time point status for target lesions, nontarget lesions, and new lesions.

Finding of new lesions should not be attributable to differences in scanning technique, change in imaging modality or findings thought to represent something other than tumor. Necrosis of pre-existing lesions as part of a response to treatment should be excluded before defining a 'new' cystic lesion. A lesion identified on a follow-up study in an anatomical location that was not scanned at baseline is considered a new lesion. If a new lesion is equivocal because of its small size, repeat scans need to confirm there is definitely a new lesion, and progression should be declared using the date of the initial scan.

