# 7.2.1 Progression-Free Survival (PFS)

#### 7.2.1.1 Definition

Duration of PFS is defined as the time from randomization to the earlier of the date of radiographic progression or date of death due to any cause.

PFS (months) =(earliest date of progression, death, censoring – date of randomization + 1)/30.4375

The primary analysis of PFS will include all subjects in the ITT population and will include radiographic progression events as determined by the investigator per RECIST 1.1 and deaths.

The recorded date of radiographic progression is the date of the tumor assessment visit at which progression is declared. If multiple scan dates are associated with a tumor assessment visit, the earliest assessment date within the set will be chosen as the progression date.

Only adequate tumor assessments (ATAs) will be considered in the determination of radiographic progression and censoring dates. For the purpose of this study, ATA is defined as one that results in a time point assignment of: response (complete or partial), stable disease/(non-CR, non-PD), or progression. For PFS, ATA is based on soft tissue evaluation by CT/MRI and/or new lesions identified by bone scan.

General censoring rules for the primary analysis of PFS are described below:

• Subjects who receive systemic or liver directed local NPACT or non-protocol radiation therapy (other than to bone) or surgery to resect tumor lesions before experiencing an

event will be right censored at the date of the last ATA on or prior to the date of initiation of subsequent therapy/surgery. If there is no such tumor assessment after randomization, the subject will be right censored on the date of randomization.

- Subjects who have not experienced an event (and are not otherwise censored) at the time of data cutoff will be right censored on the date of their last tumor assessment after randomization that is on or prior to the data cutoff. If there is no such tumor assessment after randomization, the subject will be right censored on the date of randomization.
- Subjects who miss two or more ATAs (operationally defined as 126 days without an ATA) followed by an event (progression or death) will be right censored on the date of their most-recent ATA prior to the missing assessments. If there is no such tumor assessment after randomization, the subject will be right censored on the date of randomization

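### The effusion sentence in Protocol Appendix G contradicts itself and its neighbouring rules, so benign ascites could be scored as progression at one site and not at another

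*Protocol*

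**What the plan says.** The rule is a single sentence in Protocol Appendix G, Imaging Methods, under Cytology, Histology. It begins "The cytological confirmation of the neoplastic origin of any effusion that appears or worsens during treatment", limits itself to the time when measurable tumor is in response or stable disease, and ends "will be considered malignant unless cytologically confirmed".

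Other parts of the protocol bear on the same fluid:

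- Appendix G, Definitions, lists "leptomeningeal disease, ascites, pleural/pericardial effusions" among nonmeasurable lesions, so fluid can be recorded as non-target disease.
- Appendix G, Time Point Assessments, says a new lesion should not be attributable to a "change in imaging modality or findings thought to represent something other than tumor".
- Appendix G, Definitions (nontarget lesions) and the Non-Target Lesion response table require non-target progression to be unequivocal. It must reflect the overall tumor burden or disease status rather than growth of one lesion.
- Appendix F, Liver decompensation, states "GI bleeding, hepatic encephalopathy, ascites, and bacterial infections should be treated as in patients with nonneoplastic liver disease". Appendix E scores ascites as part of Child-Pugh. Exclusion criterion 10 in section 4.3 bars only moderate or severe ascites.

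SAP 7.2.1.1 says the primary PFS analysis "will include radiographic progression events as determined by the investigator per RECIST 1.1 and deaths". The SAP has no rule of its own for effusions or ascites.

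**The concern.** The sentence starts from confirming that an effusion is neoplastic and ends by calling it malignant unless confirmed. A site that takes the closing words at face value would treat new or worsening fluid as malignant unless a cytology result intervened. In this population fluid often has another explanation, and the protocol itself says so.

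PFS and ORR are formally tested secondary endpoints (two-sided 0.04 and 0.01; Protocol 9.4, SAP 7.3), and both rest on investigator reads. If some progression calls reflect portal hypertension or liver decompensation, PFS picks up events unrelated to tumor growth, scored differently from site to site. A response could also be lost if such a call comes before the confirming scan.

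**Working it through.** No figure in the plan depends on this sentence, so there is nothing to reproduce. The check is textual, followed by an illustration of direction.

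**1. What the sentence can mean.** Its grammatical subject is the confirmation, not the effusion, and it never says what result cytology must give. Three readings are open:

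- Literal: malignant by default, with the exception falling on effusions whose neoplastic origin is confirmed. This defeats itself.
- Malignant unless cytology shows the fluid to be benign.
- Not malignant unless cytology shows tumor.

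The documents do not choose among them. The second is a natural reading for a site, because Time Point Assessments uses the same form for new bone scan lesions: malignant in the absence of contrary evidence. But the bone scan rule lets imaging or clinical data rebut the presumption. The effusion sentence mentions only cytology, and the Appendix A schedule contains no effusion cytology.

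**2. When it applies.** Only while measurable tumor is in response or stable disease. That is also when an effusion could decide the overall call.

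**3. Benign fluid is foreseeable.** Child-Pugh A is 5 to 6 points over five items (Appendix E). Slight ascites scores 2; with the other four items at 1 the total is 4 × 1 + 2 = 6, still class A. Such a subject can enter, and the ascites can worsen on study.

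**4. Route to an event.** Ascites and effusions are nonmeasurable disease. In the Overall Timepoint Response table, non-target PD or a new lesion makes the time point PD whatever the target lesions show. Investigator PD is a PFS event under SAP 7.2.1.1.

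**5. The same subject at two sites.** Target lesions are stable, slight ascites at baseline has grown, and no cytology was taken. A site following the Cytology sentence could call the fluid malignant and record progression. A site following the non-target rules could find no unequivocal progression and record stable disease. If the fluid is new, the new-lesion rule gives the second site the same ground. Nothing says which text prevails.

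**6. Downstream.** PFS2 and PFS3 (SAP 7.2.1.4, Table 3) keep every radiographic progression as an event, so neither isolates progression based on fluid alone. For ORR, SAP 7.2.2.1 takes the best category and requires confirmation at least 28 days after the response was first observed. A fluid-based PD can block a response or its confirmation but does not undo a confirmed one.

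**7. Direction, on assumed values only.** With constant hazards, let f_c and f_p be the hazards of falsely called progression on cabozantinib and placebo, as fractions of the placebo PFS hazard. Then

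observed HR = (true HR + f_c) / (1 + f_p).

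Equal in both arms (f_c = f_p = f):

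| True HR | f = 2% | f = 5% | f = 10% |
|---|---|---|---|
| 0.50 | 0.510 | 0.524 | 0.545 |
| 0.60 | 0.608 | 0.619 | 0.636 |
| 0.70 | 0.706 | 0.714 | 0.727 |

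In one arm only, at 5% and a true HR of 0.60: cabozantinib only, 0.60 + 0.05 = 0.65; placebo only, 0.60 / 1.05 = 0.571. Equal error dilutes the effect; unequal error can move it either way. The documents give no effusion rate and no PFS hazard ratio assumption, so every input here is assumed.

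**The case against.** A reader might infer that the protocol presumes every new or worsening effusion malignant and so obliges sites to score benign ascites as progression. The documents do not support that. The malignant default is one reading of a broken sentence, and the sentence is limited to response or stable disease. It speaks of malignancy, not progression. Progression is assigned only through target, non-target or new-lesion status, and those rules let an investigator reject ascites from portal hypertension. The Definitions also list ascites separately from pleural and pericardial effusions, so even its inclusion under effusion is natural rather than stated. All of this stands. It makes the fault an unresolved conflict, not a mandatory misclassification.

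Two further inferences fail. One is that the error must be worse on cabozantinib: Protocol 6.7.3 reports ALT, AST and bilirubin elevations, not ascites. The other is that the bias can be sized from the randomized-stage PFS medians in Protocol 1.3.3.3.2 (1.4 and 2.5 months). Those come from 22 subjects selected for stable disease at Week 12, in a study that started at 100 mg, with no significant difference between groups. They are not a PFS assumption for this trial.

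It is also fair to say that clinical cytology may be done although it is unscheduled, that a separate imaging manual not available here may settle the matter, that scans are collected for possible independent review (Protocol 5.7.6.1), and that PFS and ORR are tested only if OS succeeds. These points limit the consequence. None of them states in the protocol or SAP which rule a site should follow.

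**Conclusion.** The sentence is wrong as written and should be repaired. It contradicts itself, and its literal default conflicts with the new-lesion and non-target rules of the same appendix, in a population where the protocol expects ascites from liver disease. The consequence is inconsistent scoring between sites, with a possible route from benign fluid to an investigator PFS event or to an unconfirmed response. OS and already confirmed responses are untouched.

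The size and direction cannot be derived from the documents. The illustrative hazard ratios show only that equal error would dilute the PFS effect and that unequal error could go either way. They are not estimates for this trial. The conclusion rests on the text alone and assumes that no document outside the protocol and SAP already resolves the conflict.

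**What to change.** Rewrite the Cytology, Histology entry as a complete sentence that names ascites, states the default and says what cytology must show, consistent with the new-lesion and non-target rules. For example: a pleural or pericardial effusion or ascites that appears or worsens during treatment is not by itself progression when it is thought to represent something other than tumor; it counts only if cytology obtained for clinical reasons is positive for malignancy, or if there is otherwise unequivocal progression or a new lesion. Align the imaging manual if it differs, and tell the sites.

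Optionally, add a PFS sensitivity analysis that does not count progression based only on effusion or ascites. This should be fixed before unblinding, as SAP 4.8 requires, and needs the tumor assessment data to show what drove each call.

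The cost is one sentence, a site communication and, if wanted, one supportive analysis. It concerns endpoint scoring only and adds no procedure. The downside is that a few truly malignant effusions without cytology may be called progression one scan later.

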### **Time Point Assessments**

The frequency and schedule of tumor assessments is defined in the protocol. The schedule is to be maintained regardless of whether study treatment is held or discontinued.

At baseline, tumors and lymph nodes are classified and documented as target or nontarget per the definitions provided above. It is possible to record multiple nontarget lesions involving the same organ as a single item (eg, ‘multiple liver metastases’).

At all postbaseline (follow-up) evaluations the baseline classification (target, nontarget) is to be maintained and lesions are to be documented and described in a consistent fashion over time (eg, recorded in the same order on source documents).

At each assessment, a sum of the diameters (longest for nonnodal lesions, short axis for nodal lesions) for all target lesions will be calculated and included in source documents. The *baseline sum of the diameters* (SoD) will be used as reference to further characterize any objective tumor regression in the measurable dimension of the disease. The lowest SoD (nadir) since (and including) the baseline value will be used as reference for evaluating progression.

After baseline, target lesions should have the actual size documented, if possible, even if the lesions become very small. If in the opinion of the radiologist the lesion has likely disappeared, 0 mm should be recorded. If the lesion is present but too small to measure, an indicator for ‘too small to measure’ should be included in source documents.

Nontarget lesions are to be assessed qualitatively (present, resolved, or unequivocal progression) and new lesions, if any, are to be documented separately.

At each evaluation, progression status is to be determined based upon the time point status for target lesions, nontarget lesions, and new lesions.

Finding of new lesions should not be attributable to differences in scanning technique, change in imaging modality or findings thought to represent something other than tumor. Necrosis of pre-existing lesions as part of a response to treatment should be excluded before defining a 'new' cystic lesion. A lesion identified on a follow-up study in an anatomical location that was not scanned at baseline is considered a new lesion. If a new lesion is equivocal because of its small size, repeat scans need to confirm there is definitely a new lesion, and progression should be declared using the date of the initial scan.

Time point progression can be based solely on bone scans if there is unequivocal evidence of new bone scan lesions. New bone scan lesions will be considered malignant in the absence of correlative imaging or clinical data that demonstrate lesions are not malignant. Follow up imaging may be required to ensure new lesions are unequivocal. Increases in the density or size of bone scan lesions present at baseline cannot be the basis of progression.

## RESPONSE CRITERIA

---

### Target Lesion Time Point Response (TPR)

---

Complete Response (CR)	

Disappearance of all target lesions. All pathological lymph nodes (whether target or non-target) must have reduction in short axis to < 10 mm.

Partial Response (PR)	

At least a 30% decrease in SoD of target lesions, taking as a reference the baseline SoD

Stable Disease (SD)	

Neither sufficient shrinkage to qualify for PR nor sufficient increase to qualify for PD.

Progressive Disease (PD)	

At least a 20% increase in the SoD of target lesions, taking as a reference the smallest (nadir) SoD since (and including) baseline. In addition to the relative increase of 20%, the SoD must also demonstrate an absolute increase of at least 5 mm.

Not Applicable (NA)	

No target lesion identified at baseline.

Unable to Evaluate (UE)	

One or more target lesions are not imaged and the remainder of the SoD compared with the nadir SoD does not meet the criterion for PD.

---

SoD, baseline sum of diameters (longest for non-nodal lesions; short axis for nodal lesions)

If the target lesion for a subject meet the criteria for both PR and PD at a given time point, the target lesion response is PD.

If the nadir of SoD is 0 (ie, the subject had a prior target lesion CR), the reappearance of any prior target lesion to any degree constitutes PD.

---

